12.0 CONFIDENTIALITY

How will confidentiality of data be maintained? Check all that apply.

- Paper-based records will be kept in a secure location and only be accessible to personnel involved in the study.
- Use of a code number to label all research data
- Use of a study ID code linking list that will be maintained separate from the research data files on the HMC server (identifiers)
- Computer-based files will only be made available to personnel involved in the study through the use of access privileges and passwords.
- Prior to access to any study-related information, personnel will be required to sign statements agreeing to protect the security and confidentiality of identifiable information.
- Whenever feasible, identifiers will be removed from study-related information.
- A Certificate of Confidentiality will be obtained, because the research could place the subject at risk of criminal or civil liability or cause damage to the subject's financial standing, employability, or liability.
- A waiver of documentation of consent is being requested, because the only link between the subject and the study would be the consent document and the primary risk is a breach of confidentiality. (This is not an option for FDA-regulated research.)
- Precautions are in place to ensure the data is secure by using passwords and encryption, because the research involves web-based surveys.
- Audio and/or video recordings will be transcribed and then destroyed to eliminate audible identification of subjects.
- Other (specify): All data entered and stored in RedCap database (the proxy PI has an active RedCap account) and will be used to transfer data in a deidentified format only.

12.1 Identifiers associated with data and/or specimens

Identifiers like dates and medical record numbers will be used.

12.2 Use of Codes, Master List

Use of a code linking list will be maintained separate from the research data files on the HMC server. All data entered and stored in HIPAA compliant RedCap database (the proxy PI has an active RedCap account) and will be used to transfer data in a deidentified format only.

12.3 Storage of Data

All electronic files will be encrypted and/or password protected-EXCEL database, stored on a hard drive in locked HMC offices. Paper files will be stored in locked HMC offices/labs of the research team. These will be deleted/ shredded/destroyed at the end of study approval period. Information will be kept confidential and private and managed according to HIPAA guidelines.

12.4 Access to Data

Research team consisting of PI, Co-investigators, team participants, biostatisticians only will have access to the data

12.5 Transferring Data

Not applicable.

Institutional Review Board

13.0 PRIVACY

Protected health information that will be obtained includes patient name, medical record number, and date of birth. This information will be kept in a password-protected database in Excel sheet, behind the Pennsylvania State University firewall as well as the RedCap database (Co-PI has an active RedCap account). Identifying information will be stored in a separate portion of the database, linked to the analytical database through an alphanumeric code. Published data will only report aggregate, de-identified results.

14.0 DATA AND SAFETY MONITORING

All clinical information will be kept confidential, in a password-protected database or locked, secure location and managed according to HIPAA guidelines.

14.1 Periodic evaluation of data

Data evaluated at our site only.

14.2 Data that are reviewed

Data reviewed at our site only.

14.3 Method of collection of safety information

Data collected safely in a HIPAA compliant, encrypted database- Excel and REDCAP database. Access limited to PI and proxy PI and co-investigators only.

14.4 Frequency of data collection

Biweekly

14.5 Individual's reviewing the data

PI, co-investigators, and statistician from our institution only

14.6 Frequency of review of cumulative data

Every month

14.7 Statistical tests

As mentioned in detail in statistics section

14.8 Suspension of research

Unable to do workshops.

14.9 Multi-center Research

Not applicable

15.0 RISK/BENEFIT ASSESSMENT

15.1 Potential Study Risks

Minimal. It is an intervention to determine changes in mood scales before and after creative writing workshop, and we anticipate minimal risk (breach of confidentiality – measures taken as above) for patients regarding their underlying cancer or treatment.

15.2 Potential Study Benefits

Participants randomized to the intervention with creative writing workshops may experience an improvement in their mood. We suspect that patients may have better adherence to their cancer therapy, but we do not expect any effect on cancer overall.

15.3 Alternatives to Participation

Not participating.

16.0 SUBJECT COMPENSATION

No compensation will be provided. Coffee and light snacks will be served with every workshop.

17.0 NUMBER OF SUBJECTS: 60

17.1 Intervention Arm: 40

17.2 Control Arm: 20

Institutional Review Board

18.0 RESOURCES AVAILABLE

18.1 Facilities and locations

Only the patients seen at Penn State Hershey Cancer Institute will be included. PI has been involved in numerous previous studies at this location.

18.2 PI Time devoted to conducting the research

The PI will be devoted to conducting the research. The Co-PIs will have dedicated research time during their training to conduct the research. The study team will meet at biweekly intervals to review progress and provide feedback.

18.3 Availability of medical or psychological resources:

We will be collaborating with the Department of psychiatry at PSHMC - [name], [name], and [name]. Any subject who request psychiatry follow up will be referred to [name].

18.4 Process for informing Study Team

The study team will meet at biweekly intervals to review the progress of the study and to provide feedback.

19.0 ADVERSE EVENT REPORTING:

Reporting Adverse Reactions and Unanticipated Problems to the Responsible IRB

The only possible adverse event or unanticipated problem is the loss of confidentiality, and as far as loss of confidentiality is concerned, in accordance with applicable policies of The Pennsylvania State University Institutional Review Board (IRB), the investigator will report, to the IRB, any observed or reported harm (adverse event) experienced by a subject or other individual, which in the opinion of the investigator is determined to be (1) unexpected; and (2) probably related to the research procedures. Harms (adverse events) will be submitted to the IRB in accordance with the IRB policies and procedures.

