The control arm will receive a book (i.e., *Writing Down Bones* by Natalie Goldberg) on creative writing and asked to read and do writing activities for one and a half hours once every two weeks. At the completion of the two-month participation or completion of 4 sessions control patients will be given the opportunity to enroll in the creative writing workshops for the remainder of the study period of 6 months. We will collect scores from control arm through the same Emotion Thermometers Scale on a monthly basis. Pre-intervention scores will be obtained at the time of consent or one week prior to the planned start of session 1 for workshop (either in the clinic if possible or mail the score sheet to patients with an enclosed stamped envelope for return of the scales). Depending on participant preference, we can send them emails of the REDCAP surveys containing the same information at set intervals. A sample of the REDCAP surveys is included in supplementary materials. We will also send participants in the control arm a stamped return envelope on a monthly basis if not able to get score sheets in a clinic or over REDCAP, depending on patient convenience and preference. We will call the participants once every 3-4 weeks to check in on their progress. Please see a calendar at the end for details.

To assess for possible confounding results of patients participating in the concurrent exercise study, we will ask participants if they are also enrolled in the exercise study at enrollment and perform a subset analysis for patients who are in the exercise study. They will be randomized into either control or intervention group in the same manner as the other patients in the study. We will additionally include a section of the survey to ask about regular exercise (more than 30 minutes, three times a week) and do a subset analysis of these patients as well.

We will be collaborating with the Department of psychiatry at HMC - [name], [name], and [name]. Any subject who requests psychiatry follow up will be referred to [name]. If participants report the presence of suicidal ideation per question nine on the PHQ-9 [i.e., Thoughts that you would be better off dead or of hurting yourself in some way], they will be referred on an urgent basis to [name] or [name]. In the event [name] and/or [name] are unavailable for follow-up, If any active suicidal thoughts are reported, participants will be referred directly to Emergency Department at Hershey Medical Center.

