10.2 Clinical Covariates: Detailed clinical covariates will be obtained from questionnaires and medical record review including demographics (age, gender, race), cancer type and stage, psychiatric history, chemotherapy regimen and medication use.

10.3 Creative Workshop: Write from Heart: This workshop for cancer patients usually lasts one and a half hours and is broken into several parts. Usually beginning with inspirational quotes or passages from writings of respected authors, to shift mood and illuminated deeper thought and reflection. The next phase of the class consists of sharing a beautiful or whimsical object handed person to person or placed in the middle of the table to stimulate both curiosity and the senses. When participants are able to relax fully, in tranquil and focused surroundings the imagination easily transforms a bright polished stone or a glass heart with inner fractures into a metaphorical image. The technique of journaling is also encouraged in class, as a way to promote inner awareness to strengthen writing skills and to guide students to reach for their own comfort and consolation, when not in class. Within our setting, it is normal, though not mandatory that writing may lean toward the cancer experience. At the end of each series, students would have learned how to trust their artistic instincts, connect more courageously with

Institutional Review Board

the world of their emotions and transform their fears and revelations about cancer into words on the page.

10.4 Emotional Thermometers Scale: The Emotion Thermometers tool is a simple rapid modular screening tool for detection and monitoring of emotional disorders in clinical practice. It was created by [name] J Mitchell and has a simple visual-analogue design. It is easy for most patients (including older people) to understand, quick to administer and simple to score. We have already got permission from [name] J Mitchell for royalty free usage of this scale for 2 years starting from Aug, 2016 till Aug 2018. We will be getting permission from him to extend the usage for an additional 1-2 years.

10.5 Survey of Depression and Anxiety symptoms: For anxiety, we will use Generalized Anxiety Disorder 7-item (GAD-7) validated scale by Robert Spitzer et al. For depression we will use Patient Health Questionnaire 9-item (PHQ-9) validated scale by Robert Spitzer et al. Both of these scales do not require any permission for reproduction, display, distribution or usage.

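### Section 19.0 names loss of confidentiality as the only possible adverse event although section 10.1 foresees suicidal ideation, so psychological harms are left unclassified and uncounted by arm

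*Combined protocol and SAP*

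**What the plan says.** Section 19.0 (Adverse Event Reporting) opens: "The only possible adverse event or unanticipated problem is the loss of confidentiality". The same sentence then limits the reporting duty to that subject, but goes on to cover "any observed or reported harm (adverse event) experienced by a subject or other individual" if the investigator judges it unexpected and probably related to the research. The section ends without the limit: "Harms (adverse events) will be submitted to the IRB in accordance with the IRB policies and procedures". The wording is the same in all three protocol copies in the file.

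Section 15.1 takes the same view of risk: "we anticipate minimal risk (breach of confidentiality" is the only risk it names, although it does not claim that no other exists. Section 15.2 says: "Participants randomized to the intervention with creative writing workshops may experience an improvement in their mood".

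Section 10.1 plans for something else. It begins "If participants report the presence of suicidal ideation per question nine on the PHQ-9" and provides for urgent referral to psychiatry. For active suicidal thoughts, "participants will be referred directly to Emergency Department at Hershey Medical Center". Under the same section the PHQ-9 is completed monthly in both arms.

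**The concern.** A protocol that sets up an emergency route for suicidal ideation cannot also say that the only possible adverse event is a data breach. Staff reading section 19.0 cannot tell whether new suicidal ideation is an adverse event. The reporting test adds to the doubt. It covers only unexpected events, and because section 10.1 foresees suicidal ideation, a site could decide that it never qualifies.

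The second consequence is for the results. The trial will compare depression and anxiety scores between arms, and a mean can improve while a few patients get worse. Nothing planned would tell readers how many patients in each arm developed suicidal ideation or were urgently referred. Section 10.3 says participants learn to "transform their fears and revelations about cancer into words on the page", and mood is the domain the workshop is meant to change. Worsening is therefore a reasonable thing to count, whether or not it is likely.

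**Working it through.** **Step 1. Does another section repair the statement in 19.0?**

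- Section 14.3, headed as the method for collecting safety information, describes database security only.
- Section 14.7 refers to the statistics section for tests. Section 11.1 plans plots, mixed models and paired tests of scores, with no tabulation of adverse events, item 9 responses or referrals.
- Section 14.8 gives inability to hold workshops as the only reason for suspension.
- Section 9.4.3 compares emergency room visits and hospitalisations by arm, but section 10.1 splits them only by whether they are cancer related. A visit for suicidal thoughts would be unlabelled among the non-cancer visits, and a referral to outpatient psychiatry would not appear.

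None of these classifies a psychological harm or counts it by arm.

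**Step 2. What could a count show?** The arm sizes are 40 and 20 (section 11.2). The plan states no figure to reproduce here. With no events among n patients, the exact two-sided 95% upper limit is 1 − 0.025^(1/n).

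| Evaluable share (assumed) | Workshop | Control |
|---|---|---|
| 100% | 0/40: 8.8% | 0/20: 16.8% |
| 90% | 0/36: 9.7% | 0/18: 18.5% |
| 80% | 0/32: 10.9% | 0/16: 20.6% |

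**Step 3. How many events might there be?** The documents give no rate, so 2%, 5% and 10% per patient are assumptions. Expected patients are 40p and 20p. The chance of at least one event among all 60 is 1 − (1 − p)^60.

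| p | Workshop (40p) | Control (20p) | At least one in 60 |
|---|---|---|---|
| 2% | 0.8 | 0.4 | 70% |
| 5% | 2 | 1 | 95% |
| 10% | 4 | 2 | 99.8% |

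**Step 4. How many would need an IRB report?** Only events that are unexpected and probably related. If a share q of events met that test (also an assumption), the chance of at least one reportable event is 1 − (1 − pq)^60. With q = 10% this is 11%, 26% and 45% for the three rates. With q = 20% it is 21%, 45% and 70%. The last column of step 3 therefore concerns any event, not a reportable one.

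**The case against.** The strongest reply is that the two sections can coexist. Section 10.1 describes the response to a screening item and does not say that the workshop causes suicidal ideation. Section 6.1 expects background depression up to three times the general rate, and section 19.0 is concerned with events probably related to the research. It also defers to IRB policies that are not in the file and may settle classification. This limits the point, but it does not rescue a sentence saying that nothing else is possible.

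Foreseeability can also be overstated. Section 10.3 says that writing about cancer is optional, and the abstract says the programme is more about creative writing than about cancer. In the pilot (section 5.2), scores were lower after class than before it at each visit. That stands: the documents give no ground for inferring that the workshop does harm.

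A reader might also infer that patients with suicidal ideation go without care. They do not. Section 7.4 excludes uncontrolled depression, section 10.1 provides referral and calls every 3-4 weeks, and section 14.6 provides monthly review of cumulative data. Nor is IRB reporting barred, given "any observed or reported harm (adverse event) experienced by a subject or other individual" and the closing sentence of section 19.0.

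Much of the information is collected anyway. Item 9 is stored monthly, so a count could be made later. Referrals outside the Emergency Department are what might be lost. The visible text mentions no referral log, but the REDCap sample and the calendar cannot be seen, so its absence cannot be confirmed.

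**Conclusion.** The statement in section 19.0 is wrong as written and should be corrected. Followed literally, it leaves psychological harms unclassified, and no section plans a count of them by arm. Care of patients, the endpoints, the primary analysis and the sample size are not affected.

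The conclusion rests on the text, not on an event rate. The 2-10% rates are illustrative. It is tempting to read the 70% to 99.8% in step 3 as the chance that an IRB report will be needed, but the documents do not support that, because neither the rate nor the share of events meeting the reporting test is known. The planned table would be imprecise: zero-event upper limits are 8.8% (0/40) and 16.8% (0/20), and wider with missing data. It would be informative as a description and too weak to compare arms.

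**What to change.** 1. **Section 19.0:** delete the claim that only one adverse event is possible, and the lead-in confining the duty to confidentiality. The existing unexpected and probably related test then applies to any harm, including psychological harm.
2. **Log:** record (a) new or worsened suicidal ideation after baseline, whether from item 9 (including a rise in patients already positive at baseline) or voiced in class or on a call; and (b) urgent psychiatric or Emergency Department referrals for it, entered as actions taken and not as separate adverse events. Entry in the log does not depend on the reporting test.
3. **Table:** by randomised arm, give the number of patients whose item 9 score is above their own baseline, over patients with a baseline and at least one later PHQ-9 in the window. Show new and worsened cases separately, with exact 95% intervals and no test.
4. **Window:** use the same scheduled PHQ-9s in both arms before controls may join workshops. Under section 10.1 that is months 1 and 2, with month 2 completed before joining. If the three months of sections 9.2 and 11.1 are kept, use months 1 to 3. List later events separately.
5. **Separate listings:** show voiced events and referrals made at the patient's own request apart from the table, because workshop patients have more contact with staff.
6. **Section 15.1:** add possible psychological distress, and add it to the consent form if it is not already there. The consent pages are not visible.

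Item 9 is already collected, so the new work is the wording, the log and one descriptive table. The downsides are a few more events to assess, many of them reflecting background illness, wide intervals, and probably a minor IRB amendment with consent wording.

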22.0 TABLES and FIGURES for the STUDY**Table 1: DEMOGRAPHICS**

Participant	1	2	3	4	5	6	7...
Serial Number							
Alphanumeric code							
Medical Record Number							
Gender							
Age							
Living Alone vs with family/caretaker							
Primary Cancer Type							
Cancer Stage							
ECOG Performance Status							
Enrolled in the Exercise Study							
Regular exercise on or off the exercise study- >30mins three times a week							
Current Treatment (Surgery, Radiation, Chemo)							
Disease status at completion of study (Stable, Progression, Remission)							
Psychiatric history (previous diagnoses or hospitalizations)							
Current Psychiatric Medications							

Figure 1: Emotion Thermometer Score (ETS)

Emotion Thermometers 5 items+help

Instructions: In the first four columns, please mark the number (0-10) that best describes how much emotional upset you have been experiencing in the past week, including today. In the last column please indicate how much you need help for these concerns.

1. Distress	2. Anxiety	3. Depression	4. Anger	5. Need Help
 An orange thermometer with a scale from 0 to 10. The bulb at the bottom is orange and the stem is orange. The top of the stem has three orange radiating lines. The number 10 is at the top and 0 is at the bottom.	 A green thermometer with a scale from 0 to 10. The bulb at the bottom is green and the stem is green. The top of the stem has three green radiating lines. The number 10 is at the top and 0 is at the bottom.	 A blue thermometer with a scale from 0 to 10. The bulb at the bottom is blue and the stem is blue. The top of the stem has three blue radiating lines. The number 10 is at the top and 0 is at the bottom.	 A red thermometer with a scale from 0 to 10. The bulb at the bottom is red and the stem is red. The top of the stem has three red radiating lines. The number 10 is at the top and 0 is at the bottom.	 A grey thermometer with a scale from 0 to 10. The bulb at the bottom is grey and the stem is grey. The top of the stem has three grey radiating lines. The number 10 is at the top and 0 is at the bottom.
Extreme				Desperately
None				Can manage by myself

Are you already getting help for these problems? N/A No Yes Do you want further help for these problems? No Yes

Alex J Mitchell © 2013

Figure 2: Somatic Symptom Scale

Somatic Symptom Scale – 8 (SSS-8)

During the past 7 days , how much have you been bothered by any of the following problems?					
	Not at all	A little bit	Somewhat	Quite a bit	Very much
Stomach or bowel problems	0	1	2	3	4
Back pain	0	1	2	3	4
Pain in your arms, legs, or joints	0	1	2	3	4
Headaches	0	1	2	3	4
Chest pain or shortness of breath	0	1	2	3	4
Dizziness	0	1	2	3	4
Feeling tired or having low energy	0	1	2	3	4
Trouble sleeping	0	1	2	3	4

I, the copyright holder of this work, hereby publish it under the following licenses:

Permission is granted to copy, distribute and/or modify this document under the terms of the [GNU Free Documentation License](#), Version 1.2 or any later version published by the Free Software Foundation; with no Invariant Sections, no Front-Cover Texts, and no Back-Cover Texts.

This work is licensed under the [Creative Commons Attribution-ShareAlike 4.0 License](#).

You may select the license of your choice.

Figure-3**PATIENT HEALTH QUESTIONNAIRE-9
(PHQ-9)**

Over the last 2 weeks , how often have you been bothered by any of the following problems? (Use "✓" to indicate your answer)	Not at all	Several days	More than half the days	Nearly every day
1. Little interest or pleasure in doing things	0	1	2	3
2. Feeling down, depressed, or hopeless	0	1	2	3
3. Trouble falling or staying asleep, or sleeping too much	0	1	2	3
4. Feeling tired or having little energy	0	1	2	3
5. Poor appetite or overeating	0	1	2	3
6. Feeling bad about yourself — or that you are a failure or have let yourself or your family down	0	1	2	3
7. Trouble concentrating on things, such as reading the newspaper or watching television	0	1	2	3
8. Moving or speaking so slowly that other people could have noticed? Or the opposite — being so fidgety or restless that you have been moving around a lot more than usual	0	1	2	3
9. Thoughts that you would be better off dead or of hurting yourself in some way	0	1	2	3

FOR OFFICE CODING 0 + _____ + _____ + _____
=Total Score: _____

If you checked off any problems, how difficult have these problems made it for you to do your
work, take care of things at home, or get along with other people?

Not difficult at all 	Somewhat difficult 	Very difficult 	Extremely difficult 
---	---	---	--

Developed by Drs. Robert L. Spitzer, Janet B.W. Williams, Kurt Kroenke and colleagues, with an educational grant from Pfizer Inc. No permission required to reproduce, translate, display or distribute.

Figure - 4

GAD-7				
Over the last 2 weeks , how often have you been bothered by the following problems? (Use "✓" to indicate your answer)	Not at all	Several days	More than half the days	Nearly every day
1. Feeling nervous, anxious or on edge	0	1	2	3
2. Not being able to stop or control worrying	0	1	2	3
3. Worrying too much about different things	0	1	2	3
4. Trouble relaxing	0	1	2	3
5. Being so restless that it is hard to sit still	0	1	2	3
6. Becoming easily annoyed or irritable	0	1	2	3
7. Feeling afraid as if something awful might happen	0	1	2	3
(For office coding: Total Score T   =   +   +  )				

Developed by Drs. Robert L. Spitzer, Janet B.W. Williams, Kurt Kroenke and colleagues, with an educational grant from Pfizer Inc. No permission required to reproduce, translate, display or distribute.

Institutional Review Board

Dear Reviewers,

We wanted to bring your attention to 1 protocol change we have completed that we describe below.

1. **The Enrollment Period** has been extended from 3 months to 4-5 months after initiation of study

Rational: Difficulty with participant accrual.

Our enrollment period is based on the last day individuals can enroll and still complete the requested number of classes. Previously, for a 6-month class schedule with a request for 3 months of participation, we would enroll for three months. By changing the requested participation to 2 classes/month in two months as described by the previous amendment, we can extend the enrollment period by two additional weeks while still having individuals be able to complete the necessary number of classes.

Detailed description of changes

The following changes have been made in the document "**HRP-591 Protocol for Human Subjects Research – Study 00008646 Creative Writing Study – IRB – Amendment 1 protocol v3 tracked edits 8.30**" – you can see these same changes on the Tracked Changes version of the protocol as well:

- 1) **Section 9.2 Design**, first paragraph, sentence 3
 - changed three to "four-month period"
- 2) **Section 9.5 Study Schema, Figure 1:**
 - edited study schema to reflect enrollment for 4-5 months
- 3) **Section 10.1 Methods**
 - Changed enrollment from 1st 3 months to 1st 4-5 months

